3.6.2 Full Analysis Set

The Full Analysis Set (FAS) will be used for the analysis of seizure data (efficacy) and will consist of all subjects in the SS who have a minimum of 2 hours of interpretable VEEG data from both the Baseline period and the first 3 hours of the post-Baseline period after initial BRV treatment.

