8.1 Endpoint definitions and derivations

8.1.1 BRV responder and non-responder definitions

A BRV responder is defined as a subject who achieves the following reduction in seizure burden (ENS in minutes per hour) without need for rescue medication, compared to the seizure burden measured during the Baseline Period immediately prior to BRV administration, evaluated for a 2-hour period starting 1 hour after the start of initial BRV treatment:

- At least 80% reduction (≥ 80 percent change) in non-severe seizure burden
(Non-severe seizure burden is defined as $\leq 50\%$ seizure activity on video-electroencephalography (VEEG) in all 30-minute timespans)

OR

- At least 50% reduction (≥ 50 percent change) in severe seizure burden

(Severe seizure burden is defined as >50% seizure activity on VEEG in any 30-minute timespan. Timespans of 30 minutes refer to the following intervals within the 2-hour period: 0 to \leq 30 minutes, >30 to \leq 60 minutes, >60 to \leq 90 minutes, and >90 to \leq 120 minutes.)

Subjects not meeting the BRV responder definition are classified as BRV non-responders. In addition, subjects who drop out due to lack of BRV efficacy, are switched over to another AED treatment, or are administered any rescue medication (any treatment initiation with a new AED, or any increase of dose or frequency of an existing concomitant AED for the treatment of seizures during the Evaluation Period - including BZDs) during the first 3 hours after initiation of BRV treatment will be considered BRV non-responders.

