8.1.4 Average per hour seizure burden (ENS in minutes per hour)

Average per hour seizure burden per subject (ENS in minutes per hour) is defined as total seizure burden measured over a period of time (in minutes) divided by the number of hours in the given period of time. That is all seizure activity times (durations in minutes) will be added up across the Evaluation Period. It will then be divided by the total duration of the Evaluation Period to calculate a seizure burden value in minutes per hour. Average seizure burden value will be calculated during the Baseline period and the Evaluation Period (and transformed the data by taking log (x +1) for both Baseline and the Evaluation Period if needed).

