- Absolute reduction in average seizure burden measured by continuous VEEG from Baseline to the end of the 96-hour Evaluation Period [*derivations*: see the definition of baseline seizure burden and of average per hour seizure burden in [Section 8.1](#), average per hour over 96-hour Evaluation Period seizure burden is calculated as the total seizure burden during the 96-hour Evaluation Period divided by 96, the number of hours in the Evaluation Period, average per hour seizure baseline seizure burden is calculated as the total seizure burden over 1-hour Baseline Period divided by 1. The **absolute reduction** in average per hour seizure burden is defined as the average per hour seizure burden at the end of the 96-hour Evaluation Period minus average per hour baseline seizure burden]

- Percentage reduction in average seizure burden measured by continuous VEEG from Baseline to the end of the 96-hour Evaluation Period [**derivations**: see the definition of baseline seizure burden and of average per hour seizure burden in [Section 8.1](#), average per hour over 96-hour Evaluation Period seizure burden is calculated as the total seizure burden during the 96-hour Evaluation Period divided by 96, the number of hours in the Evaluation Period, average per hour seizure baseline seizure burden is calculated as the total seizure burden over 1-hour Baseline Period divided by 1. The **percentage reduction** is defined as the absolute reduction in average per hour seizure burden divided by the average per hour baseline seizure burden and multiplied by 100.]
- Proportion of BRV responders during the 96-hour Evaluation Period (measured at the end of the 96-hour Evaluation Period) [**derivations**: see the definition of BRV responders for other than main efficacy variable in [Section 8.1](#), the post-baseline seizure burden will be evaluated during the last 1 hour of the 96-hour Evaluation Period, the denominator is defined as the number of subjects in the FAS from Confirmatory Cohorts.]

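### Unrecorded VEEG time in post-dose hours 1–3 counts as seizure-free: the FAS window and the response window differ, and burden is divided by nominal rather than recorded hours

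*SAP*

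**What the plan says.** Three rules in the SAP bear on the main secondary efficacy variable.

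- **Who is analysed.** SAP 3.6.2, repeated in Protocol 13.1, requires a "minimum of 2 hours of interpretable VEEG data from both the Baseline period and the first 3 hours of the post-Baseline period". The post-dose window is the whole of "the first 3 hours of the post-Baseline period after initial BRV treatment"; the rule sets no minimum for any part of those 3 hours.
- **When response is judged.** SAP 8.1.1 has burden "evaluated for a 2-hour period starting 1 hour after the start of initial BRV treatment", that is, hours 1–3. The thresholds are "At least 50% reduction (≥ 50 percent change) in severe seizure burden" or "At least 80% reduction (≥ 80 percent change) in non-severe seizure burden".
- **How burden is averaged.** SAP 8.1.4 takes total seizure minutes "divided by the number of hours in the given period of time". For the Evaluation Period it adds: "It will then be divided by the total duration of the Evaluation Period". SAP 8.2.4 puts a number on this for the 96-hour variables, "divided by 96, the number of hours in the Evaluation Period", and divides the Baseline total by 1.

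Recording gaps are expected. Protocol 5.1 allows 30 minutes of interruption per day and accepts longer ones for standard-of-care needs, while asking sites to try to avoid them during Baseline and the first 3 post-dose hours.

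No rule says how a gap is treated. SAP 4.2 imputes only dates and times for medications and adverse events. The observed-hours rule in SAP 4.2.3 is for dropouts. The sensitivity analysis in SAP 8.2.3 covers dropout, switching and rescue medication.

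**The concern.** Entry to the FAS can be earned partly with hour 0–1, which plays no part in the response. A subject recorded in hours 0–2, or in hours 0–1 and 2–3, satisfies the post-dose clause with only 60 of the 120 response minutes observed. If the seizure minutes from those 60 minutes are then divided by 2 hours, the missing hour enters the calculation as an hour without seizures.

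The result affected is the main efficacy result. Protocol 13.5.1 compares the 95% CI of this responder rate, with all Confirmatory Cohorts combined, with the historical rate to decide whether BRV is called efficacious. If all 36 planned subjects were in the FAS, each reclassified subject would move the rate by 1/36 = 2.8 percentage points.

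**Working it through.** The plan states no figure for this point to reproduce. The inputs are the thresholds in SAP 8.1.1, the averaging rule in SAP 8.1.4 and the percent-change formula in SAP 8.1.5: 100 × (Baseline − post-dose) / Baseline, both in minutes per hour.

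**Formula.** Let B be the Baseline rate over a fully recorded hour, q the true proportional reduction (rate steady across hours 1–3), and g the unrecorded minutes inside hours 1–3.

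- Recorded seizure minutes = B(1 − q)(120 − g)/60.
- Dividing by the nominal 2 hours gives B(1 − q)(1 − g/120).
- Apparent reduction = 1 − (1 − q)(1 − g/120).
- True reduction needed to reach threshold T = 1 − (1 − T)/(1 − g/120).

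| Gap inside hours 1–3 (min) | Apparent reduction if nothing changed | True reduction needed, severe (T = 50%) | True reduction needed, non-severe (T = 80%) |
|---|---|---|---|
| 0 | 0% | 50% | 80% |
| 15 | 12.5% | 42.9% | 77.1% |
| 30 | 25.0% | 33.3% | 73.3% |
| 45 | 37.5% | 20% | 68% |
| 60 | 50.0% | 0% | 60% |

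**Examples with a 60-minute gap in hours 1–3 and a full 1-hour Baseline**

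- Severe, 40 min/h before and after: 40/2 = 20 min/h; (40 − 20)/40 = 50.0%, a responder. By recorded time: 40/1 = 40 min/h, 0.0%, a non-responder.
- Non-severe, 20 falling to 8 min/h: 8/2 = 4 min/h; (20 − 4)/20 = 80%, a responder. By recorded time: 8/1 = 8 min/h, 60%, a non-responder.

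**Position of the gap.** Severe subject, unchanged rate, 60-minute gap starting at 0 h: 0% apparent reduction. Starting at 0.5 h: 25%. Starting anywhere from 1 h to 2 h: 50%.

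**The 3-hour variables in SAP 8.2.4.** If the period length is again the divisor, one lost hour with an unchanged rate gives 60/180 = 33.3% apparent reduction.

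**Status epilepticus Baseline of 30 minutes, 20 seizure minutes recorded (true rate 40 min/h).** With the 1-hour Baseline divisor, B = 20/1 = 20 min/h.

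- Unchanged rate, 60-minute post-dose gap: 40/2 = 20 min/h; (20 − 20)/20 = 0%, a non-responder. The two errors cancel.
- Rate truly halved, no gap: 40 minutes over 2 h = 20 min/h; again 0%, a non-responder despite a true 50% reduction. Response would need 10 min/h or less, a true reduction of (40 − 10)/40 = 75%.
- If Baseline is instead divided by 0.5 h, B = 40 min/h, and the unchanged subject with the 60-minute gap is back at 50.0%, a responder.

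**The case against.** A reader might infer that any severe subject with one unrecorded hour and no improvement is scored a responder, and that the plan always favours BRV. The documents do not support either statement.

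- **The hour must fall inside hours 1–3.** An hour lost in 0–1 changes nothing.
- **The unchanged case sits on the threshold.** A rise from 40 to 40.1 min/h gives 49.8% after the truncation in SAP 8.1.5, a non-responder. The band of true reductions from 0% to just under 50% is the more robust statement.
- **Baseline length matters.** Severe means more than 15 seizure minutes in a 30-minute block (SAP 8.1.2.2). Status epilepticus means 15 minutes within 30 (SAP 2.3.2). Every severe subject therefore meets the status definition, for which the planned Baseline is up to 30 minutes. There the 1-hour divisor cancels the post-dose error or works against BRV. A full hour remains possible, since earlier standard-of-care VEEG may be used.
- **The divisor is not spelled out for the 2-hour window.** Nominal hours are the plain reading of SAP 8.1.4 and are explicit for the 96-hour variables and their Baseline, but hours 1–3 have no worked divisor.
- **The FAS sentence has a second defect.** Read per period, it asks for 2 hours from a Baseline of 1 hour or less, which would exclude the example subject altogether. Read as a total, the position is worse: 1 hour of Baseline plus hour 0–1 would qualify with nothing recorded in hours 1–3, and 0/2 scores as a 100% reduction.
- **Frequency is unknown.** The protocol asks sites to avoid gaps in this window, and the documents give no expected rate.

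These points limit the claim without removing it. None supplies a rule for unrecorded time, and the non-severe example does not depend on status epilepticus.

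**Conclusion.** The point holds in limited form. The post-dose FAS rule and the response window do not match, and on the plain reading of SAP 8.1.4 time unrecorded within hours 1–3 counts as seizure-free.

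With a fully recorded 1-hour Baseline and a steady post-dose rate, a 60-minute gap lowers the required true reduction from 50% to 0% (severe) and from 80% to 60% (non-severe). A 30-minute gap, no longer than the daily allowance, lowers it to 33.3% and 73.3%. The post-dose error on its own favours BRV. The same divisor on a short Baseline works the other way, so the net direction across the trial cannot be stated. The 2.8 points per subject is the weight of one subject among 36, not an estimate of bias.

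This should be corrected before the analysis: two programmers could score the same subject differently, and the variable feeds the historical comparison.

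**What to change.** 1. **Divisor.** In SAP 8.1.4, 8.1.5 and 8.2.4, divide seizure minutes by interpretable VEEG hours, at Baseline and in every post-dose window, including the 3-hour and 96-hour variables. This is the essential change: a recording minimum alone that tolerates a 30-minute gap would still let a true 33.3% reduction pass in a severe subject.
2. **Analysis set.** In SAP 3.6.2 and Protocol 13.1, set the post-dose recording minimum within hours 1–3. The threshold is the sponsor's choice. In the same sentence, bring the 2-hour Baseline requirement into line with the 1-hour or up-to-30-minute Baseline.
3. **Reporting.** Report the subjects below the minimum, and add a sensitivity analysis that counts them as non-responders.

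The cost is SAP and protocol wording, with no new data collection. The downside is that a few subjects may be not evaluable in the main analysis. Dividing by recorded time also assumes that the unrecorded minutes resemble the recorded ones, which is why the minimum and the sensitivity analysis are needed alongside it.

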3.6.3 Pharmacokinetic Per Protocol Set

The Pharmacokinetic Per-Protocol Set (PK-PPS) will consist of all subjects who provide at least one measurable post-Baseline plasma sample (with recorded sampling time) on at least 1 post-Baseline visit with documented study medication intake times. This analysis set will be used for the Exploratory Cohort and the Confirmatory Cohort(s). Subjects with important protocol deviations will be excluded from the PK-PPS.

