13.1 Definition of analysis sets

Analysis sets will be defined as follows:

- The Pharmacokinetic Per-Protocol Set will consist of all subjects who provide at least 1 measurable plasma sample (with recorded sampling time) on at least 1 post-Baseline visit with documented study drug intake times. This analysis set will be used for the Exploratory Cohort and the Confirmatory Cohort(s).
- The SS will consist of all enrolled subjects who take at least 1 dose of BRV. All safety analyses will be performed on the SS for the Exploratory Cohort and the Confirmatory Cohort(s).
- The Full Analysis Set will be used for the analysis of seizure data (efficacy) and will consist of all subjects in the SS who have a minimum of 2 hours of interpretable VEEG data from both the Baseline period and the first 3 hours of the post-Baseline period after initial BRV treatment.

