13.6 Handling of protocol deviations

Important protocol deviations are deviations from the protocol that could potentially have a meaningful impact on key PK, efficacy, or safety outcomes for an individual subject. The criteria for identifying important protocol deviations and the classification of important protocol deviations will be documented in a protocol-defined specification document. To the extent feasible, rules for identifying important protocol deviations will be defined without review of the data and without consideration of the frequency of occurrence of such deviations. Whenever possible, criteria for identifying important protocol deviations will be implemented algorithmically to ensure consistency in the classification of important protocol deviations across all subjects.

Important protocol deviations will be reviewed as part of the ongoing data cleaning process prior to database lock to confirm exclusion from analysis sets.

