3.5 Protocol deviations

Important protocol deviations (IPD) are deviations from the protocol that could potentially have a meaningful impact on key PK, efficacy, or safety outcomes for an individual subject. The criteria for identifying important protocol deviations and the classification of IPDs will be documented in a protocol-defined specification document. To the extent feasible, rules for identifying IPDs will be defined without review of the data and without consideration of the frequency of occurrence of such deviations. Whenever possible, criteria for identifying IPDs will be implemented algorithmically to ensure consistency in the classification of IPDs across all subjects.

Important protocol deviations will be reviewed as part of the ongoing data cleaning process prior to database lock to confirm exclusion from the Pharmacokinetic Per-Protocol Set.

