5.2 Protocol deviations

The number and percentage of FAS subjects with no important protocol deviations and at least 1 important protocol deviation will be summarized overall, and by main category of protocol deviation (Inclusion criteria deviation, Exclusion criteria deviation, Withdrawal criteria deviation, Prohibited concomitant medication, use incorrect treatment or dose, Treatment non-compliance, Procedural non-compliance). Additionally, the number and percentage of subjects excluded from the PK-PPS due to important protocol deviations will be summarized overall and by main protocol deviation category for the FAS. Other specific categories of protocol deviations will be defined within the IPD specifications document.

Listing of subjects excluded from PK-PPS will be provided.

Listing of important protocol deviations will be provided for the SS.

All completed COVID-19 Impact eCRF pages and other IPDs will be discussed in IPD meetings, including whether the deviation may have been caused by COVID-19.

All data collected from the COVID-19 Impact eCRF page will be listed only.

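### The SAP does not limit exclusion from the PK set to deviations that affect PK, so valid first-dose concentrations could be dropped from the primary summaries

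*SAP*

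**What the plan says.** Protocol 13.1 defines the PK-PPS as "all subjects who provide at least 1 measurable plasma sample (with recorded sampling time) on at least 1 post-Baseline visit", with documented dosing times. It contains no exclusion for protocol deviations. Protocol 13.6 says, in general terms, that important deviations are reviewed before lock "to confirm exclusion from analysis sets"; it names no set and sets no PK restriction.

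SAP 3.6.3 keeps the sample requirement and adds: "Subjects with important protocol deviations will be excluded from the PK-PPS". SAP 3.5 defines important deviations as those that "could potentially have a meaningful impact on key PK, efficacy, or safety outcomes for an individual subject". They are to be "reviewed as part of the ongoing data cleaning process prior to database lock to confirm exclusion from the Pharmacokinetic Per-Protocol Set". On where the detail sits, SAP 3.5 states: "The criteria for identifying important protocol deviations and the classification of IPDs will be documented in a protocol-defined specification document". The main categories in SAP 5.2 include prohibited concomitant medication and "Treatment non-compliance, Procedural non-compliance", none of them restricted to PK.

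The primary PK variable (Protocol 4.1.1, SAP 2.2.1.1) is the BRV plasma concentration after the first dose on Day 1. SAP 9.1 produces PK summary tables and listings on the PK-PPS. SAP Table 3.1, which records changes to protocol-defined analyses, does not mention the added exclusion.

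**The concern.** A deviation can matter for efficacy or safety and say nothing about whether a BRV concentration is valid. The exclusion rule does not make that distinction, and it acts on the whole subject rather than on the sample.

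The effect runs the wrong way round. The Full Analysis Set (SAP 3.6.2) has no deviation criterion. A deviation that bears only on seizure outcome would therefore leave the baby in the efficacy analysis, if the VEEG requirement is met, and remove the baby from the PK analysis.

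At stake are the SAP's descriptive summaries of the primary variable. Protocol 5.1.4 asks for at least 36 Confirmatory subjects with evaluable PK data, and SAP 2.4 says Confirmatory dropouts are not replaced. The hypothermia sub-analysis of PK may rest on as few as 2 babies per cohort, so losing one could halve that group. The SAP names no wider set on which BRV concentrations would still be shown; the Safety Set listing in SAP 10.5 covers other AEDs' plasma levels.

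**Working it through.** **The plan's own figure.** Protocol 5.1.4 gives at least 42 evaluable subjects: 6 + 3 × 12 = 42, which reproduces. Protocol 13.9 states that no formal sample size calculation was made, so there is no power or precision figure to check. The point is textual; the arithmetic below only illustrates size.

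**Following the text through**

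1. SAP 3.5: impact on PK, efficacy or safety is enough to make a deviation important, so an efficacy-only deviation can qualify.
2. SAP 3.6.3: subjects with important deviations leave the PK-PPS. No condition links the deviation to PK.
3. SAP 9.1: PK tables and listings use the PK-PPS. A subject outside it contributes no BRV concentration to them.
4. SAP 3.6.2: the same subject is not removed from the Full Analysis Set.

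**A concrete case.** Protocol 7.8.2 bars Confirmatory subjects from changing concomitant seizure treatment in the first 3 hours after the first BRV dose, and from starting LEV at any time after BRV is introduced. Prohibited concomitant medication is a main deviation category in SAP 5.2. Suppose such an event is classified as important. The first PK sample is due 30 to 60 minutes after the start of infusion (Protocol Table 5–5). A change of seizure medication at 2 hours, or LEV started on Day 3, cannot alter a sample already drawn. Because exclusion is by subject, that sample is dropped with the rest.

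**Illustrative size.** Neither document gives a rate of important deviations. Assume that 10% to 25% of the 36 Confirmatory subjects have one unrelated to PK, and that each leads to exclusion.

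- Subjects lost: 0.10 × 36 = 3.6, about 4; 0.25 × 36 = 9.
- Subjects left: 36 − 4 = 32; 36 − 9 = 27.
- Width of a 95% CI for a mean relative to N = 36, SD unchanged: [t(0.975, n − 1)/√n] ÷ [t(0.975, N − 1)/√N].

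| n | t(0.975, n − 1) | t/√n | Ratio to N = 36 |
|---|---|---|---|
| 36 | 2.030 | 0.338 | 1.00 |
| 32 | 2.040 | 0.361 | 1.07 |
| 27 | 2.056 | 0.396 | 1.17 |

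**The case against.** The strongest reply is that exclusion is not automatic. SAP 3.5 has deviations reviewed before lock to confirm exclusion, which implies judgement case by case. SAP 5.2 reports Full Analysis Set subjects with at least one important deviation and, in addition, says that "the number and percentage of subjects excluded from the PK-PPS due to important protocol deviations will be summarized overall"; under an automatic rule the two counts would be largely redundant. The specification document, which is not available here, may already separate PK-relevant deviations. This stands against the stronger reading that a reader might infer, namely that every subject with any important deviation is certain to be lost. It does not remove the point. The review has no stated PK criterion, and the unqualified sentence in SAP 3.6.3 gives a reviewer no written basis for keeping a subject. If selective exclusion is intended, SAP 3.6.3 does not say so.

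Second, Protocol 13.6 already foresees exclusion from analysis sets, so the SAP may be carrying out the protocol rather than contradicting it. That is fair. The gap is narrower: Protocol 13.1 contains no such exclusion for this set, and Table 3.1 does not record the addition.

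Third, the example depends on classification. Protocol 7.8.3 allows rescue medication at any time if the investigator considers it necessary and handles use in the first 3 hours as nonresponse, whereas Protocol 7.8.2 does not permit a change in that window. Those passages must be reconciled before anyone can say whether such a change is a deviation at all.

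Fourth, exclusions would be visible: SAP 5.2 counts them by category and lists them. This helps transparency but does not restore the concentrations to the summaries.

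**Conclusion.** The point holds as a conditional one. SAP 3.6.3 read with 3.5 permits, and on its face requires, removal of valid BRV concentrations for deviations that have nothing to do with PK, and no stated criterion prevents it. Whether this happens depends on such a deviation occurring in a subject with a usable sample, being classified as important, and being confirmed as an exclusion.

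The range of 4 to 9 Confirmatory subjects, with CIs 1.07 to 1.17 times as wide, rests on an assumed rate of 10% to 25% and on every such deviation leading to exclusion. No figure can be derived from the documents themselves.

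Three further inferences are tempting but not supported:

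- **Loss of 1 of 6 Exploratory subjects from an AED change.** Protocol 7.8.1 permits concomitant AEDs at any time in that cohort and efficacy is not analysed there, so that deviation does not arise. Exploratory subjects may also be replaced for lack of data.
- **Selective loss of sicker babies.** This is plausible, because rescue follows poor seizure control, but it is an inference that the documents do not establish.
- **Damage to the dosing recommendations.** These come from a population PK model under a separate Data Analysis Plan (Protocol 13.3.2). Its data set is not described here, so the effect on it is unknown.

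**What to change.** Replace the last sentence of SAP 3.6.3 with wording such as: *Subjects, or where possible only the affected samples, will be excluded from the PK-PPS solely for important protocol deviations classified, before concentrations are reviewed, as affecting the BRV dose given, infusion time, sampling time or sampling line.*

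Add a PK-relevance column to the deviation specification, so that the pre-lock review in SAP 3.5 has a criterion to apply. Record the exclusion in SAP Table 3.1: even in this narrower form it departs from Protocol 13.1, which has no deviation exclusion.

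The cost is one SAP sentence, one table row, one column in the specification and a small amount of extra classification work before lock. No additional data are needed.
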